4.6.4. Physical Examination

Physical examination results at each time point will be summarized using shift tables to indicate change in status (normal/abnormal) from baseline to each post-baseline assessment.

Those findings on physical examination that represented a changes from baseline will be presented in by-subjec tdata listing for each treatment group.

4.6.5. Electrocardiogram

Electrocardiogram (ECG) parameters include the heart rate, PR interval, QRS interval, QT interval, QT interval corrected for heart rate according to Fredericia's formula (QTcF), sinus rhythm (yes/no), overall ECG interpretation by the investigator or designee (normal, abnormal clinically not significant and abnormal clinically significant) and comments from the overall ECG interpretation by the investigator or designee.

The ECG recording obtained at screening will represent the baseline for all on-treatment observations.

Actual values and changes from baseline in ECG intervals and the heart rate will be summarized by descriptive statistics and presented in tables and by-subject listings for each treatment group. Categorical analysis of the QT and QTcF intervals (absolute value \leq 450, 451-480, 481-500, and $>$ 500 msec and change from baseline $<$ 30, 31-60, and $>$ 60 msec) will also be performed and frequencies (number and percent of subjects) in each category will be presented in tables and by-subject listings for each treatment group. The specific value for each subject will be provided in the listing of categorical analysis results.

The overall ECG assessment results will be summarized by category (normal, abnormal clinically not significant, abnormal clinically significant) in frequency tables for each treatment group. In addition, the overall ECG assessment results will be listed by category for each treatment group. For abnormal clinically significant result, the corresponding AE term and CTCAE grade will be specified in the listing, if available.

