1.3.4. Study Procedures

The schedules of assessments for the main study are provided in Table 1 (Core Study) and Table 2 (Repeat Dosing). The schedule of assessments for the extension study is presented in Table 3.

Table 1: Schedule of Assessments – Main Study Cycle 1 – Parts 1 and 2

Assessment	Qualification Screen	MT-3724 Infusion Schedule							Safety Assessment	Safety Assessment Part 1 ONLY	Final Safety Assessment
	Visit 1 Day -28 to Day -1	Visit 2 Day 1 Dose 1	Visit 3 Day 3 Dose 2	Visit 4 Day 5 Dose 3	Visit 5 Day 8 Dose 4	Visit 6 Day 10 Dose 5	Visit 7 Day 12 Dose 6	Visit 8 Day 16-19 (If early withdrawal, must still be performed)	Visit 9 Day 23-25 (If early withdrawal, must still be performed)	(If withdrawing replaces Day 28 safety assessment prior to Cycle 2) Day 28-35	
Informed Consent	X										
Inclusion/Exclusion	X										
Medical History Review and Physical Exam including ECOG¹	X	X								X	
Baseline Disease Assessments	X										
Vital Signs²	X	X	X	X	X	X	X	X	X	X	
Concomitant Medications	X	X	X	X	X	X	X	X	X	X	
Adverse Events	X	X	X	X	X	X	X	X	X	X	
Clinical Laboratory CBC w/differential	X	X		X (post infusion)				X	X	X	
Serum Chemistry	X	X						X	X	X	
B2 microglobulin	X									X	
Serum Rituximab	X										
For CLL subjects ONLY: soluble CD23 and thymidine kinase 1	X									X	
For CLL subjects ONLY: anti-globulin test	X										

Assessment	Qualification Screen	MT-3724 Infusion Schedule							Safety Assessment	Safety Assessment Part 1 ONLY	Final Safety Assessment
	Visit 1 Day -28 to Day -1	Visit 2 Day 1 Dose 1	Visit 3 Day 3 Dose 2	Visit 4 Day 5 Dose 3	Visit 5 Day 8 Dose 4	Visit 6 Day 10 Dose 5	Visit 7 Day 12 Dose 6	Visit 8 Day 16-19 (If early withdrawal, must still be performed)	Visit 9 Day 23-25 (If early withdrawal, must still be performed)	(If withdrawing replaces Day 28 safety assessment prior to Cycle 2) Day 28-35	
PT, aPTT, INR	X										
Urinalysis	X									X	
Estimated Cr Clearance ³	X								X	X	
Pregnancy Test (urine) ⁴	X	X (-72 hrs)									
Complement (CH50 and C3)	X										
Quantitative Serum Immunoglobulins	X									X	
Viral Serology: HepBAb HepBsAg HepCAb and/or HIV if clinically indicated	X										
Flow Cytometry , Lymphocyte subsets ⁵	X				X (pre-infusion)				X	X (including MRD analysis for CLL)	
Serum Cytokines ⁶	X	X		X					X	X	
MT-3724 Administration⁷		MT-3724	MT-3724	MT-3724	MT-3724	MT-3724	MT-3724				
MT-3724 Serum Levels (PK)⁸		X (pre- and post-infusion)		X (post-infusion)	X (pre-infusion)		X (post-infusion)		X	X	

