During the Repeat Dosing Study, at the first visit starting each cycle, an ADA/immunogenicity sample should be drawn prior to the initiation of MT-3724 infusion and a PK sample should be drawn at 5 minutes (+1 minute) following the end of that infusion. Whenever an unscheduled ADA/immunogenicity sample is drawn for clinical indication(s), a serum PK sample should be drawn concurrently.

During Cycles 2 - 5, at the first visit starting each cycle, an ADA/Immunogenicity sample should be drawn prior to the initiation of MT-3724 infusion and a PK sample should be drawn at 5 minutes (+1 minute) following the end of that infusion. Whenever an unscheduled ADA/Immunogenicity sample is drawn for clinical indication(s), a serum PK sample should be drawn concurrently.

Final Safety Assessment: A single MT-3724 serum PK sample will be obtained concurrent with the immunogenicity (ADA) sample no matter how many doses have been administered (all cycles). Additional samples may be requested if indicated.

⁹ Serum samples for ADA/Immunogenicity will be collected during the **Core Study** during Screening (Day -28 to -1) or on Dose Day 1 prior to initiation of dosing and at the Visit 9 Safety Assessment 11 to 14 days following the sixth dose of the first course (Day 23-25). Additional ADA/immunogenicity samples will be obtained pre-dose on Day 1 of each Repeat Dosing Study cycle and at the **Final Safety Assessment** 14-28 days following infusion of the final dose in the **Core Study or Repeat Dosing Study**. For subjects who withdraw early, a serum ADA/Immunogenicity sample will be collected at the Final Safety Assessment 14-28 days following their last infusion. **Additional samples may be requested if clinically indicated**. Additional ADA/immunogenicity samples obtained for any “clinical indication” should have a PK sample obtained at the same time.

¹⁰ Standard 12-lead ECG printouts will be obtained at screening, during Cycle 1 ([Table 5](#)) on Day 1 (Visit 2, Dose 1) within 3 hours prior to initiation of dosing and then at 1 hour (\pm 15 min) and 2 hours (\pm 15 min) post start of infusion. For Cycles 2-5, standard 12-lead ECG printouts will be captured at any time it is clinically indicated.

¹¹ See Study Protocol Appendix 3. CT scans will be performed for disease assessment. Where clinically indicated, PET scan will also be performed per investigator discretion.

Table 3: Schedule of Assessments – Extension Study

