3.4. Baseline Definitions

For both the Main and Extension studies, unless noted otherwise, baseline will be defined as the most recent measurement prior to the first administration of MT-3724 in the Main Study.

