4.6.3. Vital Signs

Vital signs parameters include systolic and diastolic blood pressure, heart rate, respiration rate, body temperature and body weight.

The actual value and change from baseline within each on-study evaluation will be summarized by treatment group. The pre-dose measurement will act as baseline for a given visit; post-dose measurements will be compared to pre-dose measurements within each visit.

Vital sign measurements will be presented for each subject in a data listing by treatment group.

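### SAP 4.6.5 takes the screening ECG as QTc baseline although a same-day pre-dose ECG is collected, which can add noise to the Day 1 changes, and its change categories leave 30 msec unclassified

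*SAP*

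**What the plan says.** SAP Section 4.6.5 (Electrocardiogram) sets the ECG baseline: "The ECG recording obtained at screening will represent the baseline for all on-treatment observations". Change from that baseline in QT and QTcF is then tabulated by treatment group in three categories, printed as <30, 31-60 and >60 msec. Absolute values are tabulated as <=450, 451-480, 481-500 and >500 msec.

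Four other places in the SAP bear on this:

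- **Screening window (1.3.4, Table 1).** The screening visit is "Visit 1 Day -28 to Day -1".
- **ECG schedule (1.3.4, footnote 10).** Besides screening, ECGs are taken in Cycle 1 "on Day 1 (Visit 2, Dose 1) within 3 hours prior to initiation of dosing and then at 1 hour" and at 2 hours after the start of infusion. After that, "For Cycles 2-5, standard 12-lead ECG printouts will be captured at any time it is clinically indicated". The extension study schedule (Table 3) likewise has ECGs only when clinically indicated.
- **General baseline rule (3.4).** For both studies, "unless noted otherwise, baseline will be defined as the most recent measurement prior to the first administration of MT-3724 in the Main Study".
- **Vital signs (4.6.3).** "The pre-dose measurement will act as baseline for a given visit".

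Section 4.6.5 does not say why screening was preferred or what use is made of the Day 1 pre-dose ECG.

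**The concern.** The 1 h and 2 h ECGs on Day 1 have a natural comparator, recorded no more than 3 hours before dosing on the same day. The SAP compares them instead with a recording from another day, possibly four weeks earlier. QTc varies within a day and may also vary between days. A same-day comparator cancels the between-day part, and a screening comparator does not. If that part is not zero, more subjects cross the 30 msec line with no drug effect, and a true shift is harder to see. Results are shown by cohort, and Part 1 cohorts were planned at 3 to 6 subjects, so one spurious shift is visible in a cohort percentage.

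The category limits are a separate matter. A change of exactly 30 msec is neither below 30 nor in 31-60, so the programmer would have to place it without a rule.

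**Working it through.** The SAP states no sample size, error rate or variability for the ECG analysis, so there is no planned figure to reproduce. Two checks were made.

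**1. Noise in the Day 1 change, with no drug effect**

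Inputs from the SAP: baseline at screening, Day -28 to Day -1 (4.6.5 and Table 1); pre-dose, 1 h and 2 h ECGs on Day 1 (footnote 10); a category boundary near 30 msec and one at 60 msec (4.6.5).

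Assumptions, not in the documents: one ECG per time point; normal errors; within-day SD sw of 6 to 10 msec; between-day SD sb from 0 up to sw.

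Formulas:

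- SD of change from same-day pre-dose = sqrt(2 sw²)
- SD of change from screening = sqrt(2 sw² + 2 sb²)
- P(change > c) = 1 − Φ(c / SD)

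Example at sw = sb = 10: the SDs are sqrt(200) = 14.1 and sqrt(400) = 20.0 msec. For c = 30, the screening baseline gives 1 − Φ(1.5) = 6.7%, and the pre-dose baseline gives 1 − Φ(30/14.1) = 1.7%.

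| sw | sb | SD, pre-dose | SD, screening | >30 msec, pre-dose | >30 msec, screening |
|---|---|---|---|---|---|
| 6 | 6 | 8.5 | 12.0 | 0.02% | 0.6% |
| 8 | 0 | 11.3 | 11.3 | 0.4% | 0.4% |
| 8 | 5 | 11.3 | 13.3 | 0.4% | 1.2% |
| 8 | 8 | 11.3 | 16.0 | 0.4% | 3.0% |
| 10 | 0 | 14.1 | 14.1 | 1.7% | 1.7% |
| 10 | 5 | 14.1 | 15.8 | 1.7% | 2.9% |
| 10 | 10 | 14.1 | 20.0 | 1.7% | 6.7% |

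Rates are per subject and time point. With sb = 0 the two baselines perform the same. With sb = sw the SD is sqrt(2) = 1.41 times as large from screening.

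For the larger of the 1 h and 2 h changes (1,000,000 simulated subjects per setting), the rate above 30 msec is 4.9% from screening against 0.8% from pre-dose at 8/8, and 10.2% against 3.1% at 10/10.

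For c = 60 at 10/10, screening gives 1 − Φ(3) = 0.13% and pre-dose about 0.001%. Even with sb raised to 12 at sw = 10, outside the range above, the screening figure is 0.33%. The false shifts therefore sit almost entirely in the 31-60 band.

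In a cohort of six at 10/10, the expected false shifts above 30 msec per time point are 6 × 6.7% = 0.40 from screening and 6 × 1.7% = 0.10 from pre-dose.

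**2. Category limits**

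Every integer change from −100 to 199 msec was assigned to the printed categories. Only 30 falls in none. Any value from 30 to below 31, such as 30.4, is also unassigned. The absolute categories miss no integer, but decimals such as 450.5 or 480.5 have no category. QTcF comes from a formula, so decimals can arise, and 4.6.5 sets no rounding rule.

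**The case against.** **A reader might infer that 4.6.5 contradicts 3.4.** It does not. The general rule opens with an allowance for exceptions, and 4.6.5 is one. What stands is that the exception is unexplained and differs from the SAP's treatment of vital signs.

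**The size rests wholly on assumed SDs.** This is correct. No variability figure is given, and with no between-day component there is nothing to gain. For these Day 1 ECGs the pre-dose baseline is never noisier under the model, so the direction holds wherever between-day variance exists.

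**A reader might infer that false changes above 60 msec are inflated too.** The calculation does not support that to any practical extent: about 0.13% at 10/10. The absolute QT and QTcF categories do not use baseline at all.

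**The benefit is narrow.** It reaches the 1 h and 2 h ECGs on Cycle 1 Day 1. For unscheduled ECGs in later cycles or the extension, a Day 1 baseline also comes from another day and removes no between-day noise.

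**A reader might infer that the Part 4 QT/QTc objective is at risk.** The documents do not support this. This SAP is based on protocol v7.0 (Parts 1 and 2) and the extension protocol, and plans no formal tests. The Part 4 objective belongs to protocol v11.0, where ECGs are triplicate (8.4.8) and the safety baseline is the last valid value before study drug (9.3.3).

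**The category gap is a drafting slip with a safeguard.** Section 4.6.5 lists each subject's specific value, so a 30 msec change would still be reported. It would be missing from the frequency table, or placed there by an unstated decision.

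**Conclusion.** The point holds as a minor improvement. The SAP passes over a same-day pre-dose ECG that it already schedules, without giving a reason. For the two scheduled post-dose ECGs on Cycle 1 Day 1 this adds whatever between-day variance QTc has. Over the assumed range (within-day SD 6-10 msec, between-day SD from 0 up to the within-day SD), the cost runs from nothing to a false rate above 30 msec of 6.7% rather than 1.7% per subject and time point. The size depends entirely on those assumed SDs. The analysis is descriptive, so no test or decision rule in the SAP depends on it.

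The gap at 30 msec needs no assumption: it follows from the category limits as printed.

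**What to change.** In SAP 4.6.5:

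- Define the ECG baseline as the last ECG before the first infusion of MT-3724, which is the Day 1 pre-dose recording, with the screening ECG used only if that recording is missing. This follows the default in 3.4.
- Write the change categories as <=30, >30 to 60 and >60 msec.
- Write the absolute categories as <=450, >450 to 480, >480 to 500 and >500 msec. Integer results are classified as before, and decimals then have a place.

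The cost is SAP wording and the matching table specifications. The ECGs are already in the schedule, so no new data are needed.

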4.6.6. Concomitant Medications

Concomitant medications will be coded using the WHO Drug Dictionary. Results will be tabulated by anatomic therapeutic class (ATC) and preferred term.

Concomitant medications will be tabulated by treatment group, where any medications that did not end prior to first dose will be included. If an end date is missing or the medication is ongoing, the medication will be included.

The concomitant medication dates and terms will be presented in by-subject listings for each treatment group.

4.6.7. ECOG Performance Status

ECOG performance status will be summarized using a shift table to indicate change in score from baseline to each post-baseline assessment.

All ECOG data will be presented in a by-subject data listing for each treatment group.

5. CHANGES TO PLANNED ANALYSES

Changes from Version 1.0 to Version 2.0 of this SAP was the result from a change in CRO providing biostatistical services to Molecular Templates for Study MT-3724_NHL_001_US.

Changes from Version 2.0 to Version 3.0 of this SAP are the result from the changes that occurred between Protocol Version 4.0 and Protocol Version 7.0 for Study MT-3724_NHL_001_US and between Protocol Version 1.0 and Protocol Version 2.0 for Study MT-3724_NHL_001_US_EXT.

